5.3. Visit Windows

CMR and technetium scintigraphy assessments will be conducted at baseline and Month 12 in the 12m-DB period and at Months 18, 24, 36, and 48 in the OLE period. For patients randomized to placebo, if the scheduled Month 12 assessment is not performed prior to the first dose of patisiran in the OLE period, assessments performed within ± 3 months of the scheduled assessment (eg, from an unscheduled visit) and prior to the first dose of patisiran in the OLE period will be grouped with the scheduled Month 12 assessments for analysis. The same windowing for Month 12 will be applied for patients randomized to patisiran, with the exception that assessments performed up to 6 weeks after the first dose of patisiran in the OLE period will be grouped with the scheduled Month 12 assessments for analysis; this window was extended since these endpoints for patisiran patients are not expected to be meaningfully impacted within a short time after the first dose in the OLE period. For assessments in the OLE period, if a scheduled post-baseline assessment is not performed, assessments performed within ± 3 months of the scheduled assessment will be grouped with the scheduled Month 18, 24, 36, or 48 assessments for analysis. The derived visits will be used for all analyses.

5.4. Missing Data

No data imputation will be performed for missing CMR and technetium scintigraphy endpoints.

5.5. Analyses for the Entire Study

The study design includes a 12m-DB period and an OLE period. The objective in this imaging analysis is to evaluate the efficacy of patisiran compared with placebo on manifestations of cardiac amyloid involvement during the 12m-DB period. In addition, the long-term efficacy of patisiran during the entire patisiran treatment period (beyond 12m-DB) will be characterized for the CMR All Patisiran Treated Set and the Technetium All Patisiran Treated Set. Longitudinal efficacy parameters will be summarized over the entire study, including the 12m-DB and OLE periods, for all patients to show the long-term efficacy of patisiran (for patients randomized to patisiran) as well as to show the trajectory changes comparing the placebo experience versus the patisiran experience (for patients randomized to placebo). In these summaries, patients will be analyzed according to the treatment to which they were randomized during the 12m-DB period.

Detailed definitions for different treatment periods and windowing rules are specified in the APOLLO-B SAP (Section 5.11). For CMR and technetium assessments, if a patient randomized to patisiran does not have a Month 12 assessment prior to the first dose of patisiran in the OLE period, assessments collected up to 6 weeks after the first OLE dose will be grouped with the Month 12 assessments for analysis.

6. STATISTICAL ANALYSES

6.1. Patient Disposition

For all analysis sets, the patient disposition will be summarized similarly as specified in the APOLLO-B SAP (Section 6.1).

6.2. Demographics and Baseline Characteristics

For all analysis sets, demographic and baseline characteristics, baseline disease characteristics, baseline efficacy parameters, and medical history information will be summarized and listed similarly as specified in the APOLLO-B SAP (Section 6.2).

6.3. Drug Exposure

For all analysis sets, the duration of study drug exposure and number of doses of study drug received will be summarized and listed similarly as specified in the APOLLO-B SAP (Section 6.4).

6.4. Efficacy Analyses

6.4.1. Global Average Extracellular Volume

The primary CMR endpoint is the change from baseline to Month 12 in global average ECV.

The primary analysis will be performed using an analysis of covariance (ANCOVA) model for the CMR Analysis Set. All available data will be included in the primary analysis. The outcome variable is the change from baseline in global average ECV, and the model includes baseline global average ECV as a continuous covariate and treatment arm as a fixed term. If the number of patients in either treatment arm is less than 15, descriptive statistics may be presented.

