2.2. Randomization Methodology

Using the interactive response system (IRS), patients will be randomized 1:1 to the patisiran or placebo arm. Randomization will be stratified by:

1. Baseline tafamidis (yes vs. no)
2. Type of amyloidosis (hATTR vs. wtATTR amyloidosis with cardiomyopathy)
3. New York Heart Classification (NYHA) Class I or II **and** age < 75 years vs. all other

Patients in the baseline tafamidis use category are defined as patients who are currently on tafamidis (for ≥ 6 months) with disease progression in the opinion of the investigator at baseline.

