6.6.3. Exploratory Endpoints

All analyses of exploratory endpoints will be conducted on the FAS. For continuous endpoints, descriptive statistics will be provided for actual value and change from baseline by treatment arm; descriptive statistics for percentage change from baseline by treatment arm may also be provided, as appropriate.

The composite endpoint of all-cause mortality and frequency of CV events (CV hospitalizations and urgent HF visits) over the 12m-DB period will be analyzed using a modified Andersen-Gill model similar to that for the composite endpoint of all-cause mortality and frequency of all-cause hospitalizations and urgent HF visits (see Section 6.6.2.4). The frequency of CV events component will also be analyzed using Poisson regression with treatment, baseline tafamidis (yes vs. no), type of amyloidosis (hATTR vs. wtATTR), baseline NYHA class (I/II vs. III), age at randomization (<75 vs. ≥75 years), and the treatment-by-baseline tafamidis use interaction as covariates, adjusting for duration of follow-up.

The change from baseline at Month 12 in select echocardiographic parameters (mean left ventricular [LV] wall thickness, LV relative wall thickness, LV mass, LV end-diastolic volume, global LV longitudinal strain, and cardiac output) and Norfolk QoL-DN Total Score (see Section 9.3.2) will be analyzed using an ANCOVA model since they are only measured in the 12m-DB period at Month 12. The ANCOVA model will include the baseline value for the

parameter as a continuous covariate and treatment arm, baseline tafamidis use (yes vs. no), type of amyloidosis (hATTR vs. wtATTR), age at randomization (<75 vs. ≥75), and the treatment-by-baseline tafamidis use interaction as covariates. The Norfolk QoL-DN questionnaire is a patient-reported outcomes measure that is sensitive to the different features of diabetic neuropathy; since patients enrolled in this study are not required to have a history of neuropathy, the ANCOVA model for Norfolk QoL-DN Total Score may be repeated on the subset of patients with a history of neuropathy.

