5.1. Determination of Sample Size

CMR and technetium scintigraphy assessments are planned to be conducted in approximately 60 patients and up to 100 patients, respectively.

For the change from baseline at Month 12 in global average ECV (%), assuming a mean treatment difference of -4.8 between patisiran and placebo in the treatment-naïve group and -3.0 in patients with baseline tafamidis, the weighted average treatment difference between patisiran and placebo in the overall population is approximately -4.3 (standard deviation = 4.6), assuming 70% are in the treatment-naïve group and 30% are in the baseline tafamidis group. A sample

size of 60 patients provides >90% power for a 2-sided test to detect a mean difference between treatment arms at a 2-sided alpha = 0.05.

For the change from baseline at Month 12 in normalized LV total uptake, assuming a mean treatment difference of -15.0 between patisiran and placebo in the treatment-naïve group and -9.4 in patients with baseline tafamidis, the weighted average treatment difference between patisiran and placebo in the overall population is approximately -13.3 (standard deviation = 14.0), assuming 70% are in the treatment-naïve group and 30% are in the baseline tafamidis group. A sample size of 100 patients provides >90% power for a 2-sided test to detect a mean difference between treatment arms at a 2-sided alpha = 0.05.

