6.4.2. Normalized LV Total Uptake

The primary technetium scintigraphy endpoint is the change from baseline to Month 12 in normalized LV total uptake.

The primary analysis will be performed in the Technetium Analysis Set using an ANCOVA model similar to the model described for the primary analysis of global average ECV while adjusting for baseline normalized LV total uptake as a continuous covariate. If the number of patients in either treatment arm is less than 15, descriptive statistics may be presented.

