6.4. Efficacy Analyses

6.4.1. Global Average Extracellular Volume

The primary CMR endpoint is the change from baseline to Month 12 in global average ECV.

The primary analysis will be performed using an analysis of covariance (ANCOVA) model for the CMR Analysis Set. All available data will be included in the primary analysis, including data collected post tafamidis drop-in (see APOLLO-B SAP, Section 5.6.1). The outcome variable is the change from baseline in ECV, and the model includes baseline ECV as a continuous covariate and treatment arm and baseline tafamidis use (yes vs. no) as factors.

A sensitivity analysis excluding data collected from patients after taking tafamidis for more than 28 days (see APOLLO-B SAP, Section 5.6.1) will be conducted using the same ANCOVA model as used for the primary analysis.

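### The imaging ANCOVAs leave out baseline tafamidis, a randomisation factor, without a stated reason; adding it is a free and modest improvement

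*SAP*

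**What the plan says.** For the Month 12 change in global average ECV, Imaging SAP 6.4.1 states that "the model includes baseline global average ECV as a continuous covariate and treatment arm as a fixed term". Section 6.4.2 analyses normalised LV total uptake "using an ANCOVA model similar to the model described for the primary analysis of global average ECV", with its own baseline value. Tafamidis appears in neither model.

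Elsewhere the plan takes account of it:

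- Main SAP 2.2 lists baseline tafamidis use first among the three stratification factors.
- Imaging SAP 5.1 builds the overall effects from separate effects in the two tafamidis groups, "assuming 70% are in the treatment-naïve group and 30% are in the baseline tafamidis group".
- Main SAP 6.6.3 analyses echocardiographic parameters, also exploratory and measured once after baseline in the double-blind period, by an ANCOVA with "baseline tafamidis use (yes vs. no), type of amyloidosis (hATTR vs. wtATTR), age at randomization" and a treatment-by-tafamidis interaction.

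Nothing puts the factor back into the imaging models. Imaging SAP section 5 refers to the main SAP for stratification factors, but main SAP 5.5 only settles which recorded value to use when a factor is already a covariate. The change table in Imaging SAP section 7 does not mention the point. The superseded Imaging SAP had "treatment arm and baseline tafamidis use (yes vs. no) as factors"; that is background only, since departing from superseded text is not an error.

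**The concern.** Imaging is optional and done at selected sites (Imaging SAP 1 and 2), and missing images are not imputed (5.4). The analysed set is therefore a part of the trial that was not itself stratified, and balance across the whole trial does not guarantee balance within it. If tafamidis predicts the imaging change, an uneven split between arms shifts the realised treatment estimate, and a model without the factor leaves explainable variation in the residual. Inference is allowed down to 15 patients per arm, where uneven splits are more likely. A reader of a small-subset result would ask about tafamidis balance first, and a prespecified term answers that without post hoc adjustment.

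**Working it through.** **Inputs from Imaging SAP 5.1.** ECV: effects -4.8 (naïve) and -3.0 (tafamidis), SD 4.6, 60 patients. Uptake: -15.0 and -9.4, SD 14.0, 100 patients. Mix 70/30, two-sided alpha 0.05. Allocation is 1:1 (main SAP 2.2), so 30 and 50 per arm.

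**The plan's own figures.**

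- Weighted effects: 0.7 × (-4.8) + 0.3 × (-3.0) = -4.26; 0.7 × (-15.0) + 0.3 × (-9.4) = -13.32. These match the stated -4.3 and -13.3.
- ECV: SE = 4.6 × √(2/30) = 1.19; 4.3/1.19 = 3.62; power 95.2% (normal) or 94.5% (noncentral t).
- Uptake: SE = 14.0 × √(2/50) = 2.80; 13.3/2.80 = 4.75; power 99.7%.

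Both exceed 90%, as stated.

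**Chance imbalance.** With a 30% tafamidis share and participation unrelated to arm, treating the subset as simply randomised gives an SD of the between-arm difference in share of √(0.3 × 0.7 × 2/n): 11.8 points at 30 per arm, 9.2 at 50 and 16.7 at 15. Exact binomial probabilities:

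| Per arm | Gap of 10 points or more | Gap of 20 points or more |
|---|---|---|
| 30 | 0.48 | 0.12 |
| 50 | 0.33 | 0.04 |
| 15 | 0.55 | 0.32 |

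These are upper-side figures, because stratified randomisation carries some balance into the subset.

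**Shift in the unadjusted estimate.** This is the imbalance times g, the effect of tafamidis on the change itself. The documents give no value for g, so it is an assumption. For ECV, a 20-point gap gives 0.20 × 1.8 = 0.36 at |g| = 1.8 and 0.20 × 4.8 = 0.96 at |g| = 4.8, against an assumed treatment effect of 4.3.

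**Effect of adding the factor.** Simulation with 4000 runs per setting, an uninformative baseline covariate, and the tafamidis main effect set so that the SD of the change stays near the stated value. ECV, 30 per arm:

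| Assumed g | Power without factor | Power with factor |
|---|---|---|
| 0 | 93.3% | 93.3% |
| -1.8 | 93.9% | 94.0% |
| -3.0 | 94.0% | 95.1% |
| -4.8 | 94.9% | 97.4% |

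The SD of the ECV estimate falls from 1.16 to 1.08 at g = -4.8 and is 1.22 with either model at g = 0. Uptake power at 50 per arm is about 99.6-100% with either model for g from 0 to -15. Type I error is about 4-5% throughout.

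**The case against.** The strongest reply is that nothing is invalid. A baseline-adjusted ANCOVA without a stratum term is a legitimate analysis, the endpoints are exploratory and outside the testing hierarchy, and Imaging SAP 6.2 will tabulate tafamidis use by arm, so an imbalance would be visible. At 15 per arm only about 0.3 × 15 = 4.5 patients per arm would be on tafamidis, and a sparse model can be defended. All of this stands. It limits the importance of the point, but does not show that leaving the factor out is better: one main-effect term is affordable even at 15 per arm and costs no power at 30 per arm when uninformative.

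Four stronger readings are tempting and are not supported:

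- *The estimate is biased or type I error inflated.* The shift is a consequence of chance imbalance in a given sample. On average the estimate is unbiased, and simulated type I error is nominal.
- *The power calculation depends on a tafamidis-adjusted model.* It uses tafamidis only to weight the effect, then applies one SD in a two-sample comparison.
- *The differing effects (-4.8 and -3.0; -15.0 and -9.4) show that tafamidis predicts the imaging change.* They are differences in treatment effect. A main effect does not model them, and they do not determine g.
- *Residual variance is inflated by 5-21%.* That follows from 1 + 0.21k² only if the groups differ by k = 0.5 to 1.0 SD, which is an assumption. If placebo change were equal in both groups, the stated effects would imply a 1.8-point difference in the patisiran arm only, averaging 0.9 points or 0.2 SD, and 1 + 0.21 × 0.04 = 1.008, under 1%.

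Nor do the two harms apply in full together. Imbalance matters to the extent that stratified balance is lost in the subset; an overstated standard error arises to the extent that it is kept.

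**Conclusion.** The omission is real, unexplained and out of line with the echocardiographic ANCOVA in the same trial. Its consequence is limited to exposure to chance imbalance, with an SD of at most about 12 points at 30 per arm, and some lost precision. Over assumed effects of tafamidis on the ECV change from 0 to 4.8 points, adding the factor gains 0 to about 2.5 points of power from a base already above 93%; for uptake the gain is practically nil. The imbalance figures assume a 30% tafamidis share and participation unrelated to arm. The validity of the analysis and the stated power are not in question. This is a free improvement to exploratory analyses, not the correction of a faulty one.

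**What to change.** In Imaging SAP 6.4.1, keep baseline global average ECV as a continuous covariate and replace the single treatment term with "treatment arm and baseline tafamidis use (yes vs. no) as factors". Section 6.4.2 then inherits the change, with baseline uptake as its covariate; stating the terms there as well would remove doubt. Record the change and its reason in section 7. A treatment-by-tafamidis interaction is not needed for this purpose and would be thinly supported in the smallest arms allowed. If the sponsor prefers the two-term model, it should give the reason and prespecify the adjusted model as a sensitivity analysis. The cost is one phrase and one degree of freedom; no additional data are needed.

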6.4.2. Normalized LV Total Uptake

The primary technetium scintigraphy endpoint is the change from baseline to Month 12 in normalized LV total uptake.

The primary analysis will be performed in the Technetium Analysis Set using an ANCOVA model similar to the model described for the primary analysis of global average ECV while adjusting for baseline normalized LV total uptake as a continuous covariate. If the number of patients in either treatment arm is less than 15, descriptive statistics may be presented.

6.4.3. Other CMR and Technetium Scintigraphy Parameters

All other CMR and technetium scintigraphy parameters are listed in [Table 1](#).

Table 1 Other CMR and Technetium Scintigraphy Parameters

Cardiac Magnetic Resonance	
Global percent of LGE (%)	LGE by segment (%)
Global mass of LGE (g)	T1 mapping pre-contrast by segment (ms)
Left ventricular (LV) mass (g)	Right ventricular (RV) mass (g)
LV mass index (g/m ²) [1]	RV mass index (g/m ²) [1]
LV end-diastolic volume (mL)	RV end-diastolic volume (mL)
LV end-diastolic volume index (mL/m ²) [1]	RV end-diastolic volume index (mL/m ²) [1]
LV end-systolic volume (mL)	RV end-systolic volume (mL)
LV end-systolic volume index (mL/m ²) [1]	RV end-systolic volume index (mL/m ²) [1]
LV stroke volume (mL) [2]	RV stroke volume (mL) [2]
LV stroke volume index (mL/m ²) [1]	RV stroke volume index (mL/m ²) [1]
LV ejection fraction (%) [3]	RV ejection fraction (%) [3]
LV mass to end-diastolic volume ratio (g/mL) [4]	
Cardiac output (L/min) [5]	
Cardiac index (L/min/m ²) [1]	
Left atrial (LA) reservoir emptying volume (mL)	LA reservoir emptying percent (%)
LA contractile emptying volume (mL)	LA contractile emptying percent (%)
LA total emptying volume (mL)	LA total emptying percent (%)
LA volume maximum (mL)	LA volume minimum (mL)
ECV by segment (%)	
Technetium Scintigraphy	
Heart to contralateral lung (H/CL) ratio of uptake at 3 hours post injection	Perugini grade [6]

[1] Calculated by dividing the value of the parameter listed in the row above by body surface area

[2] Stroke volume calculated as the end-diastolic volume – end-systolic volume for the LV or RV, as indicated

[3] Ejection fraction calculated as (stroke volume / end-diastolic volume) * 100 for the LV or RV, as indicated

[4] Calculated as LV end-diastolic volume / LV end-diastolic volume

[5] Calculated as heart rate * LV stroke volume

[6] Scoring algorithm for Perugini grades is provided in [Appendix 9.1](#)

The CMR Analysis Set and Technetium Analysis Set will be used to summarize all other CMR and technetium parameters for the 12m-DB period, respectively.

For continuous parameters, descriptive statistics will be provided for actual value and change from baseline by treatment arm and visit; descriptive statistics for percentage change from baseline by treatment arm and visit may also be provided, as appropriate. Categorical parameters will be descriptively summarized by treatment arm by presenting the number and percentage of patients in each category for each visit.

All CMR and technetium scintigraphy data will be presented in by-patient listings.

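### Imaging SAP Table 1 footnote [4] divides LV end-diastolic volume by itself, so the LV mass-to-volume ratio as written is always 1 (minor; footnote [5] should state its unit conversion in the same edit)

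*SAP*

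**What the plan says.** The current Imaging SAP, Section 6.4.3, Table 1, lists the CMR parameters other than the primary one, with derivations in footnotes. The row for the mass-to-volume ratio is labelled "LV mass to end-diastolic volume ratio (g/mL) [4", the bracket being the footnote mark. Footnote [4] gives the derivation: "Calculated as LV end-diastolic volume / LV end-diastolic volume". LV mass (g) and LV end-diastolic volume (mL) are separate rows of the same table.

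The table gives LV stroke volume in mL. Footnote [2] derives it from two volumes in mL: "Stroke volume calculated as the end-diastolic volume – end-systolic volume for the LV or RV, as indicated". Cardiac output is labelled in L/min, with footnote [5]: "Calculated as heart rate * LV stroke volume". Cardiac index is labelled in L/min/m². Under footnote [1] it is the parameter in the row above, which is cardiac output, divided by body surface area.

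The text after the table says that continuous parameters get descriptive statistics for actual value and change from baseline by arm and visit, with percentage change where appropriate, and that all CMR data go into by-patient listings.

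**The concern.** A derivation footnote in an analysis plan is an instruction to the programmer. Footnote [4] cannot produce the quantity its row names, because one of the two named inputs is missing and the other appears twice. A programmer who follows it reports a constant. A programmer who silently corrects it reports something sensible that departs from the approved plan with no record of why.

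This is neither a PDF-reading fault nor superseded text. The identical footnote appears in the original Imaging SAP, which was read separately. The table of changes in Section 7 of the current version does not mention it, so the error was carried forward into live text.

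Footnote [5] raises a lesser question. The relation is right, but the input and output units in the table differ by a factor of 1000 and the footnote does not state the conversion. What is at stake overall is the correctness and traceability of a few descriptive outputs, not any inference.

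**Working it through.** The plan reports no result for these parameters, so there is no figure to reproduce. The check sets the formulas against the table's own labels and units. The patient values below are illustrative assumptions; the documents give none.

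**Footnote [4]**

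Inputs from Table 1: LV mass in g, LV end-diastolic volume (EDV) in mL, target unit g/mL.

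- As written: EDV / EDV = 1, and mL / mL has no unit.
- As labelled: LV mass / EDV, and g / mL is the unit printed in the row.

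| LV mass (g) | EDV (mL) | As written | As labelled (g/mL) |
|---|---|---|---|
| 150 | 80 | 80/80 = 1.000 | 150/80 = 1.875 |
| 200 | 100 | 100/100 = 1.000 | 200/100 = 2.000 |
| 250 | 140 | 140/140 = 1.000 | 250/140 = 1.786 |

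The constant does not depend on the values chosen. Any non-zero volume divided by itself is 1, so the change from baseline is 1 − 1 = 0 and the percentage change is 0/1 = 0% for every patient.

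**Footnote [5], and footnote [1] for cardiac index**

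Inputs: stroke volume (SV) = EDV − end-systolic volume (ESV), in mL; heart rate (HR) in beats/min, whose unit the footnote does not state; target unit L/min. Beats/min × mL gives mL/min, and dividing by 1000 gives L/min. Cardiac index is cardiac output divided by body surface area (BSA).

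| HR | SV = EDV − ESV | HR × SV (mL/min) | ÷ 1000 (L/min) | BSA (m²) | Index (L/min/m²) |
|---|---|---|---|---|---|
| 60 | 90 − 45 = 45 | 2700 | 2.7 | 1.8 | 1.50 |
| 70 | 110 − 50 = 60 | 4200 | 4.2 | 1.9 | 2.21 |
| 90 | 140 − 60 = 80 | 7200 | 7.2 | 2.0 | 3.60 |

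The unconverted product differs from the labelled unit by exactly 1000. If it were placed under the L/min label unconverted, cardiac index would carry the same factor: 4200/1.9 = 2210.5 instead of 2.21. If cardiac output is first expressed in its labelled unit, cardiac index is correct without further change.

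**Reach of the error**

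- The stated imaging endpoints (Imaging SAP Section 3) are global average extracellular volume and normalized LV total uptake. Their analyses in Sections 6.4.1 and 6.4.2 use neither footnote.
- CMR is optional and done in up to 60 patients (Imaging SAP Section 2).
- The ANCOVA of cardiac output in Section 6.6.3 of the main SAP is listed among echocardiographic parameters, so the CMR footnote does not govern it.

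**The case against.** On footnote [4], the best defence is that the intent is plain. The row label names LV mass, the unit is g/mL, and LV mass is a row of the same table. A constant column of 1.00 would also be noticed in the by-patient listings. The specifications for tables, figures and listings are in a separate document that is not shown and may already have it right. All of this makes a wrong published result less likely, and it supports rating the point as minor. It does not make the footnote correct, since no reading of it yields the labelled ratio.

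On footnote [5], a reader might infer that the plan contains a 1000-fold error in cardiac output and cardiac index. The documents do not support that. Heart rate times stroke volume is the correct relation, and the table prints both the input unit and the output unit, so the conversion is determined. Section 5.2 of the main SAP says in general terms that values needing transformation to standard units will be converted, and Section 5 of the Imaging SAP adopts those general considerations. Two things remain on the other side: that general sentence gives no factor, and footnote [3] does write out its multiplication by 100 for ejection fraction. These justify stating the factor for clarity. The 1000-fold discrepancy is a risk only under literal programming that ignores the row label.

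**Conclusion.** Footnote [4] is wrong as written. It defines a g/mL ratio as a quantity divided by itself, giving 1 with zero change for all patients and visits. This follows from the formula alone and needs no outside source or assumed value. Whether a wrong number would reach a report depends on literal programming, which cannot be judged from the documents.

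Footnote [5] leaves a unit conversion unstated and is otherwise sound.

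The severity is minor. A reader might infer that a key measure of cardiac amyloid involvement is lost or that the imaging conclusions are affected. Neither follows. The Imaging SAP names only extracellular volume and LV uptake as its endpoints for that objective. Its introduction links late gadolinium enhancement, native T1 and extracellular volume to amyloid burden, but not this ratio, cardiac output or cardiac index. The affected parameters enter only descriptive summaries and listings.

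**What to change.** In Imaging SAP Section 6.4.3, Table 1:

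- Footnote [4]: calculate the ratio as LV mass (g) / LV end-diastolic volume (mL).
- Footnote [5], for clarity: calculate cardiac output as heart rate (bpm) × LV stroke volume (mL) / 1000. Cardiac index then follows from footnote [1] with no change.

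Record the correction to [4] in the Section 7 table of changes, or in the clinical study report if the database is already locked, and check that the separate output specifications and the program agree. The cost is two footnotes and one line in the change table. No design, sample size or planned test is affected.
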